8.3.5. Exposure During Pregnancy or Breastfeeding, and Occupational Exposure

Exposure to the investigational product under study during pregnancy or breastfeeding and occupational exposure are reportable to Pfizer Safety within 24 hours of investigator awareness.

8.3.5.1. Exposure During Pregnancy

Details of all pregnancies in female participants and, if indicated, female partners of male participants will be collected after the start of study intervention and until at least 5 terminal half-lives or approximately 7 to 11 days after the last dose.

If a pregnancy is reported, the investigator should inform the sponsor within [24 hours] of learning of the pregnancy and should follow the procedures outlined in [Appendix 4](#).

Abnormal pregnancy outcomes (eg, spontaneous abortion, fetal death, stillbirth, congenital anomalies, ectopic pregnancy) are considered SAEs.

8.3.5.2. Exposure During Breastfeeding

Scenarios of exposure during breastfeeding must be reported, irrespective of the presence of an associated SAE, to Pfizer Safety within 24 hours of the investigator's awareness, using the CT SAE Report Form. An exposure during breastfeeding report is not created when a Pfizer drug specifically approved for use in breastfeeding women (eg, vitamins) is administered in accord with authorized use. However, if the infant experiences an SAE associated with such a drug's administration, the SAE is reported together with the exposure during breastfeeding.

8.3.5.3. Occupational Exposure

An occupational exposure occurs when, during the performance of job duties, a person (whether a healthcare professional or otherwise) gets in unplanned direct contact with the product, which may or may not lead to the occurrence of an AE.

An occupational exposure is reported to Pfizer Safety within 24 hours of the investigator's awareness, using the CT SAE Report Form, regardless of whether there is an associated SAE. Since the information does not pertain to a participant enrolled in the study, the information is not recorded on a CRF; however, a copy of the completed CT SAE Report Form is maintained in the investigator site file.

8.3.6. Medication Errors

Medication errors may result from the administration or consumption of the investigational product by the wrong participant, or at the wrong time, or at the wrong dosage strength.

Exposures to the investigational product under study may occur in clinical trial settings, such as medication errors.

Safety Event	Recorded on the CRF	Reported on the CT SAE Report Form to Pfizer Safety Within 24 Hours of Awareness
Medication errors	All (regardless of whether associated with an AE)	Only if associated with an SAE

Medication errors include:

- Medication errors involving participant exposure to the investigational product;
- Potential medication errors or uses outside of what is foreseen in the protocol that do or do not involve the study participant.

Such medication errors occurring to a study participant are to be captured on the medication error page of the CRF, which is a specific version of the AE page.

In the event of a medication dosing error, the sponsor should be notified immediately.

Whether or not the medication error is accompanied by an AE, as determined by the investigator, the medication error is recorded on the medication error page of the CRF and, if applicable, any associated AE(s), serious and nonserious, are recorded on an AE page of the CRF.

Medication errors should be reported to Pfizer Safety within 24 hours on a CT SAE Report Form **only when associated with an SAE**.

8.4. Treatment of Overdose

For this study, any dose of PF-06826647 greater than 1600 mg of investigational product within a 24-hour time period will be considered an overdose.

Sponsor does not recommend specific treatment for an overdose.

In the event of an overdose, the investigator should:

1. Contact the medical monitor immediately.
2. Closely monitor the participant for any AEs/SAEs and laboratory abnormalities until PF-06826647 can no longer be detected systemically (at least 3 days).

CCI

4. Document the quantity of the excess dose as well as the duration of the overdose in the CRF.
5. Overdose is reportable to Safety **only when associated with an SAE**.

Decisions regarding dose interruptions or modifications will be made by the investigator in consultation with the medical monitor based on the clinical evaluation of the participant.

CCI

[Redacted]

[Redacted]

[Redacted]

CCI

[Redacted]

[Redacted]

[Redacted]

[Redacted]

[Redacted]

CCI [REDACTED]

[REDACTED]

[REDACTED]

[REDACTED]

[REDACTED]

[REDACTED]

[REDACTED]

[REDACTED]

[REDACTED]

[REDACTED]

CCI

Unless prohibited by local regulations or IRB/EC decision, participants will be asked to indicate on the consent document whether they will allow their banked samples to also be used to design and conduct research in order to gain a further understanding of other diseases and to advance science, including development of other medicines for patients. This component of the sampling banking is optional for participants; they may still participate in the study even if they do not agree to the additional research on their banked samples. The optional additional research does not require the collection of any further samples.

See [Appendix 5](#) for information regarding genetic research. Details on processes for collection and shipment of these samples can be found in the laboratory manual.

8.9. Health Economics

Medical resource utilization is not evaluated in this study. However, the study does include the EQ5D-5L, a questionnaire that assesses patient preference for a given health state and which will be utilized for cost-effectiveness/utility modeling. The EQ5D-5L is summarized below in the patient reported outcomes measures section.

8.10. Patient Reported Outcome Measures

Every effort should be made for the participant to complete all patient reported outcome (PRO) questionnaires before any other assessments except at Baseline when eligibility needs to be confirmed. All PROs should be completed in the following order: Psoriasis Symptom Inventory (PSI), Peak-Pruritus Numerical Rating Scale (PP-NRS), CCI [REDACTED] will be completed as a diary from baseline to Day 15. Post Day 15, these scales will be completed at the site. At site visits participants will complete PROs in the following order: Psoriasis Symptom Inventory (PSI), PP-NRS, CCI [REDACTED]. The amount of time required for a participant to complete the PRO questionnaires is approximately 10-25 minutes (depending on the visit and associated PROs).

Once participants meet all eligibility criteria, they will be provided a handheld device (provided by the sponsor) for the PSI (both 24-hour recall and 7-day recall), PP-NRS, and CCI [REDACTED] to be completed at home prior to first dose of the day. . All PROs are to be completed as per the time points defined in the [Schedule of Activities](#).

Delegated site staff will oversee the use of electronic Patient Reported Outcomes (ePRO) devices. Completion of PROs will be monitored for adherence. Delegated site staff will review adherence to all applicable PROs with participants at each visit and counsel as appropriate. If a participant has repeated non-adherence, the participant should be retrained on use of the device. If a participant is unable to complete ePROs due to documented technical issue or disability or other limitation (eg, difficulty with manual dexterity or vision), the participant will be permitted to enter or remain in the study and a valid alternate

CCI [REDACTED]

[REDACTED]

[REDACTED]

[REDACTED]

[REDACTED]

9. STATISTICAL CONSIDERATIONS

Detailed methodology for summary and statistical analyses of the data collected in this study is outlined here and further detailed in a statistical analysis plan (SAP), which will be maintained by the sponsor. The SAP may modify what is outlined in the protocol where appropriate; however, any major modifications of the primary endpoint definitions or their analyses will also be reflected in a protocol amendment.

9.1. Estimands and Statistical Hypotheses

9.1.1. Estimands

The primary estimand will be the population average treatment effect on PASI 90 rates at Week 16 relative to placebo without regard to compliance in the absence of prohibited medication. Measurements after the initiation of prohibited medication will be censored and treated as missing data. Missing data due to censoring, study withdrawal or other reasons will have data imputed using a control based multiple imputation strategy assuming these participants no longer receive an efficacy benefit from the IP but rather, have a response similar to participants assigned to placebo. The population based treatment effect will be the differences in the proportions of successes in each treatment arm compared to the corresponding placebo.

All other secondary continuous clinical endpoints will be analyzed using estimand E2, while all other key secondary categorical clinical endpoints will be analyzed using the primary estimand E1 as described above. CCI [REDACTED]

[REDACTED] Other estimands may be used for some of the primary and secondary endpoints as a means to examine the robustness of the results and to compare to

available literature as needed. Details of these analyses will be presented in the statistical analysis plan (SAP).

9.2. Sample Size Determination

The primary endpoint in this study is the PASI 90 response rate at Week 16. Assuming a PASI 90 response rate as 5% for the placebo group, and placebo corrected effect 35% or greater for one of the treatment groups, a total of N=128 completers are needed to ensure at least 90% power for the lower doses due to Bonferroni multiplicity adjustment with 1-sided type-I error rate of 5% and 2:1:1:2:2 allocation ratio of placebo, 50 mg, 100 mg, 200 mg, and 400 mg. The total sample size includes a sample size of 32 completers per arm for placebo, 200 mg and 400 mg, and 16 completers per arm for 50 mg and 100 mg. Accounting for a 20% chance of drop out, approximately a total of 160 participants will be enrolled in this study.

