4.3. Justification for Dose

Dose selection for this study was based on expected average inhibition of IL-12, IL-23, and IFN α as well as projected in vivo efficacy observed in psoriasis participants without significant JAK2 inhibition. Four dosing (50 mg QD, 100 mg QD, 200 mg QD and 400 mg QD) regimens of PF-06826647 and placebo were selected to explore the dose range in moderate to severe psoriasis participants given the practical considerations.

CCI [REDACTED]

[REDACTED]

CCI

Based on the exposure-response modeling with the PASI data observed up to Week 4, the projected PASI 90 response rates of 50 mg, 100 mg, 200 mg, and 400 mg were 3%, 13%, 47%, and 83% at Week 16, respectively. However, there is uncertainty in the extrapolation of response from Week 4 to Week 16. Although the projected PASI 90 response rates of 50 mg QD is low, the projected average inhibition (Table 3) based on in vitro IC₅₀ value determined by phosphorylated signal transducer and activator of transcription (pSTAT) modulation in human whole blood, red blood cell (RBC) partition ratio of 1.4 and assuming Hill coefficient of 1, the average daily inhibition of IL-12, IL-23, IFN α is approximately 82%, 69% and 79%, respectively. Considering both the projected PASI 90 response rate and the average inhibition of IL-12 and IL-23, 50 mg was selected as the lowest pharmacologically active dose that would be expected to be clinically minimally efficacious. The highest dose of 400 mg QD was selected based on practical considerations of daily tablet burden to participants and projected high degree of inhibition (>90%) of IL-12, IL-23 and IFN α (Table 3) at steady state.

Additionally, based on data observed to date in both healthy and psoriasis participants, these doses are expected to be safe and well tolerated. All the adverse events (AEs) observed in healthy participants up to 1200 mg QD for 10 days and psoriasis participants up to 400 mg QD for 28 days were mild in nature. Although, the projected average inhibition of erythropoietin (EPO) (Table 3) was 67% and a transient decrease in reticulocyte was observed in psoriasis participants at 400 mg QD, no clinically meaningful change in hemoglobin was observed at the same dose for 28 days in psoriasis participants. The long-term impact of transient decrease in reticulocytes on hemoglobin is currently unknown.

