Primary Estimand Categorical Endpoint Set	This set will include all patients in the mITT population. All data for a subject after the initiation of prohibited medications, withdrawal of either study drug or the study itself will be set to a failure. Any additional missing data will be recorded as a failure. Subjects will have either a success or failure in the dataset for all scheduled visits.
Secondary Estimand Continuous Endpoint Set	This set will include all patients in the mITT population. All data for a subject after the initiation of prohibited medications will be set to missing. Note the secondary estimand requires multiple imputation which will be performed on this dataset, the multiple imputations themselves will not be saved in the database.
Observed Efficacy Set	This set will include all patients in the mITT population and all observed data and includes all data recorded from the CRF pages. No data will be set to missing or modified from the original CRF record.

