5.1. Hypotheses and Decision Rules

Statistical inference will be made on the primary endpoint: Proportion of participants achieving PASI 90 (90% or greater improvement from Baseline) at Week 16 based on an analysis of the Primary Estimand Endpoint Set. The global null hypothesis is that there is no difference between any arm of PF-06826647 and placebo arm. The alternative hypothesis is that one of the PF-06826647 arms being tested is superior to the placebo arm at Week 16. The study will be considered positive, if this null hypothesis is rejected.

Since test statistic corresponding to each of the PF-06826647 arms are independent with each others satisfying the distributional assumption about the use of Hochberg step-up procedure, the familywise error-rate will be controlled in strong sense at the 1-sided 0.05 level for these tests with a Hochberg step-up procedure (Hochberg, A sharper Bonferroni procedure for multiple significance testing 1988)³ (Hochberg and Tamhane, Multiple Comparison Procedures 1987)⁴ (Marcus, Peritz and Gabriel 1976). The p-values from the 3 comparisons will be ordered from smallest to largest, $p[1]$, $p[2]$, and $p[3]$. Testing will begin with the largest p-value, $p[3]$, if significant at the 0.05 level that comparison and all other comparisons will be declared significant. If it is not significant, $p[2]$ will be compared to an alpha of 0.05/2, if $p[2] \leq 0.05/2$ it and all remaining hypotheses will be declared significant. If not significant, the process will continue using 0.05/3.

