Appendix 3. Statistical Methodology Details

Hochberg Testing Procedure

Consider testing null hypotheses H_{01}, \dots, H_{06} and let $p_i, i=1, \dots, 6$ denote the corresponding 1-sided p-values from the individual pairwise comparisons against the placebo arm prior to multiplicity adjustment. Furthermore, let $[1], \dots, [6]$ denote the order of the p-values so that $p[1] \leq p[2] \leq \dots \leq p[6]$. The procedure starts with the largest p-value $p[6]$ as follows:

1. If $p[6] < \alpha$ reject all null hypotheses, otherwise go to next step.
2. If $p[5] < \alpha/2$ reject hypotheses $H_{0[1]}$ through $H_{0[6]}$, otherwise go to next step.
3. If $p[k] < \alpha/(6-k+1)$, reject hypotheses $H_{0[1]}$ through $H_{0[k]}$.
4. If $p[1] < \alpha/6$, reject $H_{0[1]}$, otherwise stop and do not reject any hypotheses.

Alternatively, the unadjusted raw p-values can be read into Proc Multtest and adjusted using the HOC option in SAS's PROC MULTTEST.

```
data pvals;  
  Input Test$ Raw_P;  
Datalines;  
Test1 .xxxxx  
Test2 .xxxxx  
.....  
Test6 .xxxxx  
;  
Proc multtest pdata=pvals hoc out=new;  
run;
```

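### Protocol 9.2 claims at least 90% power for the 50 mg and 100 mg doses under Bonferroni; its own inputs give about 74% at a divisor of four and no more than about 85% at any divisor of two or more

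*Protocol*

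**What the plan says.** Protocol 9.2 assumes a 5% PASI 90 rate on placebo and a "placebo corrected effect 35% or greater for one of the treatment groups". It then says that "a total of N=128 completers are needed to ensure at least 90% power for the lower doses due to Bonferroni multiplicity adjustment", at an overall one-sided 5% error rate with 2:1:1:2:2 allocation. Placebo, 200 mg and 400 mg have 32 completers each, with "16 completers per arm for 50 mg and 100 mg". Neither the Bonferroni divisor nor the test behind the power figure is given. Protocol 9.4.1 names the unconditional exact method of Chan and Zhang for the primary analysis and leaves the multiplicity details to the SAP.

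The SAP does not use Bonferroni. Section 5.1 says that "the familywise error-rate will be controlled in strong sense at the 1-sided 0.05 level for these tests with a Hochberg step-up procedure". The family size is not settled: 5.1 says "The p-values from the 3 comparisons will be ordered from smallest to largest", Appendix 3 says "The procedure starts with the largest p-value $p[6]$ as follows", and the trial compares four doses with placebo.

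Protocol 4.3 reports that the "projected PASI 90 response rates of 50 mg, 100 mg, 200 mg, and 400 mg were 3%, 13%, 47%, and 83" percent at Week 16.

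**The concern.** The lower-dose arms are half the size of the others, and a Bonferroni adjustment lowers the alpha for each comparison. It would be surprising if 16 against 32 completers still gave 90% power for a 35-point difference after that adjustment.

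The trial is meant to support dose selection, and Protocol 4.2 includes 50 mg to find the minimal clinically efficacious dose. A reader who accepts 9.2 will take a non-significant 50 mg or 100 mg result as having at most a 10% chance of missing a true 40% response rate. If the power is lower, that result is weaker evidence against the dose than the protocol suggests.

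**Working it through.** **Inputs (Protocol 9.2).** p0 = 0.05; p1 = 0.05 + 0.35 = 0.40; n0 = 32; n1 = 16 (lower dose) or 32 (200/400 mg); overall one-sided alpha 0.05. The divisor is not stated. Four doses imply 0.05/4 = 0.0125, which is an assumption, so other divisors are shown too.

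**Sample size step.** 32 + 16 + 16 + 32 + 32 = 128, and 128/0.8 = 160. Both agree with the protocol.

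**Pooled z formula.** Power = Φ[(0.35 − z × SE0)/SE1].

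- Pooled rate: (32 × 0.05 + 16 × 0.40)/48 = 8/48 = 0.1667.
- SE0 = √[0.1667 × 0.8333 × (1/32 + 1/16)] = 0.1141.
- SE1 = √[0.05 × 0.95/32 + 0.40 × 0.60/16] = 0.1284.
- At 0.0125, z = 2.241: (0.35 − 0.2558)/0.1284 = 0.734, so power is 76.9%.
- At 0.05, z = 1.645: (0.35 − 0.1877)/0.1284 = 1.264, so power is 89.7%.

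**Unconditional exact test.** Outcomes were ordered by the pooled score statistic, and the p-value was maximised over the common null rate. Power is the summed binomial probability of the rejection region at 5% and 40%.

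| Divisor | One-sided alpha | Lower dose, exact | Lower dose, pooled z | 200/400 mg, exact |
|---|---|---|---|---|
| 1 | 0.05 | 90.8% | 89.7% | 97.5% |
| 2 | 0.025 | 84.5% | 83.7% | 95.3% |
| 3 | 0.0167 | 76.5% | 79.8% | 93.7% |
| 4 | 0.0125 | 73.7% | 76.9% | 91.8% |
| 6 | 0.0083 | 71.6% | 72.5% | 87.5% |

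For a single lower-dose comparison, the stated 90% appears only in the unadjusted row. At 0.0125 it appears for the larger arms (pooled z for 32 vs 32: 89.0%). Other approximations do not rescue the figure. The highest value found for a lower dose at any divisor of 2 or more is 85.9%, from a pooled z test evaluated by enumeration, which is not guaranteed to hold its level; the arcsine formula gives 85.1% at 0.025.

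**Hochberg over four doses.** This was simulated with a shared placebo arm, exact p-values and 1,000,000 runs. The table shows power for a lower dose whose true rate is 40%.

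| Rates in the other three doses | Power |
|---|---|
| All at 5% | 73.7% |
| Other lower dose 40%, 200/400 mg at 5% | about 76% |
| Other lower dose 5%, 200/400 mg at 47%/83% | 84.5% |
| All at 40% | 89.3% |
| Other lower dose 40%, 200/400 mg at 47%/83% | 89.9% |
| All certain to be rejected (ceiling) | 90.8% |

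The ceiling equals the unadjusted figure, because the most lenient Hochberg threshold is 0.05.

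**Dropouts as failures.** SAP 4.4 says "Any additional missing data will be recorded as a failure". With 20% dropout in every arm, the rates become 4% and 32%, with 40 against 20 participants. Bonferroni at 0.0125 gives 72% for a lower dose and 90% for 200/400 mg. Hochberg gives 72% if that dose alone works, 83% with the projected high-dose rates and the other lower dose null, 85–86% if both lower doses or all four work, and a ceiling of 87%. This is a sensitivity range: Protocol 9.1.1 (control-based imputation) and SAP 4.5 (COVID-19 discontinuations removed) treat missing data differently.

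**The case against.** **Another reading of the sentence.** It refers to the lower doses in the plural. If both have a 40% rate, the exact probability of rejecting at least one is 89.7% at 0.05/4, 92.1% at 0.05/3 and 95.4% at 0.05/2. But the same sentence assumes the effect for one treatment group. With one effective lower dose, the chance of any rejection is about 74%. The reading shows that the wording is unclear; it does not make the claim correct.

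**The divisor and test are inferred.** Neither document gives a divisor of four, and 9.2 names no test for the power figure. This is a fair reason not to treat 74% as the only possible number. It does not affect the conclusion, because every divisor of two or more and every test tried stays below 90%.

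**Bonferroni is not the rule that will be used.** Protocol 9 lets the SAP modify the plan, and the SAP uses Hochberg, which gives 89–90% when both lower doses or all four are effective. The 74% case under Hochberg needs 200 mg and 400 mg to fail, contrary to the protocol's projection. That is true, but with the projected high-dose rates and the other lower dose null the figure is 84.5%, and the ceiling leaves almost no room above 90%.

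**Little depends on it.** SAP 5.1 judges the study on the global null hypothesis. At the projected rates, at least one dose is rejected with probability 1.000 to three decimals. The protocol allocates fewer participants to 50 mg and 100 mg because it expects under 15% response there. This point stands, and it limits the severity.

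**Conclusion.** The stated power is wrong as written. For a lower dose at 40% against 5% on placebo, with 16 and 32 completers, Bonferroni power by the planned exact test is about 74% at a divisor of four and 84.5% at most for any divisor of two or more. The chance of missing a true 40% rate is then 100 − 74 = 26%, not at most 10%. Under four-dose Hochberg it is about 10% to 26%, and about 16% with the projected high-dose rates and the other lower dose null.

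The 74% and the Hochberg figures rest on a family of four, inferred from the number of doses; the failure to reach 90% under Bonferroni does not. How the sponsor arrived at 90% cannot be determined from the documents. The global test and the 200/400 mg comparisons are not affected. This should be corrected, but it does not threaten the trial's main conclusion.

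**What to change.** Restate Protocol 9.2:

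1. Give the number of comparisons and the per-comparison alpha, and make them match one family size used throughout the SAP (5.1 and Appendix 3).
2. If the family is four, report for 5% against 40% about 92% (exact) for 200/400 mg and about 74% for 50/100 mg on completers, labelled as conservative Bonferroni figures. With 20% dropouts counted as failures, these are about 90% and 72%. If another family size is chosen, use the matching row of the table.
3. Add power under the SAP's Hochberg procedure and state the rates assumed in the other arms, for example about 84% for a lower dose at 40% with 200/400 mg at 47%/83% and the other lower dose null.
4. Delete the claim of at least 90% power for the lower doses.

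The cost is a change of wording in 9.2 and agreement on the family size with the SAP. Sample size, randomisation, endpoint and test stay as they are. The sponsor gives up a more favourable planning figure.

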4. STUDY DESIGN

4.1. Overall Design

This is a Phase 2b, randomized, double blind, placebo controlled, parallel group, multicenter study in participants with moderate to severe plaque psoriasis. After a screening period of - up to 6 weeks, eligible participants will be randomized in a 2:1:1:2:2 ratio such that participants will receive placebo or either one of four PF-06826647 daily dose levels (50 mg, 100 mg, 200 mg or 400 mg) every day during the Investigational Treatment Period for 16 weeks in a blinded fashion. All participants completing the 16-week Investigational Period will continue to a 24-week non-placebo-controlled Extension Treatment Period with double blind oral daily treatment, if per the Investigator judgment the participant is compliant with study procedures and continued participation presents no safety risks. The participants continuing into the Extension Treatment Period that were originally randomized to the

200 mg and 400 mg treatment groups will continue their respective doses, while those randomized to one of the other treatment groups (including placebo) will be randomly assigned (at study baseline) to receive either 200 mg or 400 mg during the Extension Treatment Period. Participants who discontinue prior to Week 16 visit will have an Early Termination visit and will not be eligible for the Extension Period.

Approximately 160 participants (40 participants in each of the following arms: placebo, 200 mg, and 400 mg; and 20 participants in each of the following arms: 50 mg and 100 mg) will be randomly assigned to a treatment group in order to ensure a minimum of 128 evaluable participants completing Week 16 (assuming a 20% dropout rate).

The total duration of study participation will be approximately 50 weeks, including up to 6 weeks Screening Period, 16-week Investigational Treatment Period, the 24-week Extension Treatment Period and a Follow-Up visit 4 weeks after the Extension Treatment Period.

If a participant is withdrawn from investigational product (IP) treatment, the participant will proceed with the Early Termination (ET) and Follow Up visits per [Schedule of Activities](#).

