9.4.1. Efficacy Analyses

Endpoint	Statistical Analysis Methods
Primary and key secondary: PASI 90 and PASI 75 at Week 16	A landmark analysis of the composite endpoint; achieving a PASI 90 response (a score of 90% improvement from Baseline) without prohibited medication, while remaining on study and providing data. The analysis will use the mITT analysis set. Based on the definition of the composite endpoint all participants in the mITT set will have a response for all visits (ie, there is no missing data). The proportions responding and the risk difference between treated arms and their corresponding placebo arm will be analyzed using an unconditional exact method: risk differences and corresponding 2-sided unconditional exact 90% confidence intervals will be computed using the Chan and Zhang (1999) method. Multiplicity adjustment will be utilized; details of multiplicity adjustment will be provided in the SAP.

Other continuous secondary endpoints at time points specified in the [Schedule of Activities](#) including; absolute PASI, change from baseline PASI, percent change from baseline PASI, absolute and change from baseline Itch Severity Score, absolute and change from baseline Psoriasis Symptom Inventory will be analyzed as described for the E2 estimand along with descriptive statistics and possibly graphical displays. No adjustments for multiplicity will be made for these endpoints.

Other binary secondary endpoints at time points specified in the [Schedule of Activities](#) including, PASI 50, PASI 100, PGA of clear or almost clear and proportions of participants achieving a Psoriasis Symptom Inventory Score of 0 or 1 will be analyzed as described for the primary estimand along with descriptive statistics and possibly graphical displays. No adjustments for multiplicity will be made for these endpoints.

CCI [REDACTED]

All endpoints in Extension Treatment Period will be analyzed with descriptive statistics and graphical displays when appropriate. Details of the analyses of the Investigational Treatment Period and Extension Treatment Period will be included in the Statistical Analysis Plan (SAP).

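### Protocol 9.2 bases lower-dose power on completers, not on the planned mITT composite analysis, and its 90% is not met for 50/100 mg at the Bonferroni level it names

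*Protocol*

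**What the plan says.** **Sizing.** Protocol 9.2 sets the assumptions as "Assuming a PASI 90 response rate as 5% for the placebo group" and a "placebo corrected effect 35% or greater for one of the treatment groups", that is, 40% against 5%. It uses a one-sided 5% error rate with a Bonferroni adjustment and 2:1:1:2:2 allocation. It concludes that "a total of N=128 completers are needed to ensure at least 90% power for the lower doses". The completers are 32 each for placebo, 200 mg and 400 mg, and 16 each for 50 mg and 100 mg. It then adds: "Accounting for a 20% chance of drop out, approximately a total of 160 participants will be enrolled in this study". Protocol 4.1 gives the reason for randomising 160 (40 or 20 per arm) as "in order to ensure a minimum of 128 evaluable participants completing Week 16 (assuming a 20% dropout rate". The synopsis and SAP 2.2 say the same.

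**Primary analysis.** Protocol 9.4.1 uses the mITT set, meaning all randomised participants who took a dose. A response requires staying on study, supplying data and taking no prohibited medication. "Based on the definition of the composite endpoint all participants in the mITT set will have a response for all visits", so nothing is missing by definition. SAP 4.4 builds the data set to match: data after prohibited medication or "withdrawal of either study drug or the study itself will be set to a failure", and other missing values are failures too. SAP 6.1.1.1 applies the Chan and Zhang exact method to that set.

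**Passages that differ.** Protocol 9.1.1 describes control-based multiple imputation for the same estimand. SAP 4.5 removes participants who discontinue because of COVID-19 and applies no non-responder imputation to missing remote-visit data. On multiplicity, SAP 5.1 replaces Bonferroni with Hochberg and lists three p-values. SAP Appendix 3 lists six. The trial has four active arms.

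**The concern.** Section 9.2 treats dropout only as lost sample size: it powers on completers and divides by 0.8. The planned analysis keeps dropouts in the denominator as non-responders. Inflating enrolment restores the number of completers, but it does not turn a completer response rate into a composite one. The printed power and the 35-point effect therefore describe an analysis that the trial will not run, unless the assumed rates already count dropouts as failures. Section 9.2 is silent on that.

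The study is meant to support dose selection. A reader who takes 90% and 35 points as properties of the primary estimand may misjudge what a non-significant 50 mg or 100 mg comparison means.

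**Working it through.** **Inputs.** From Protocol 9.2: 5% and 40%, one-sided 5%, Bonferroni, 32 and 16 completers, 20% dropout. From Protocol 4.1: 40 and 20 randomised. With four active doses, Bonferroni gives 0.05/4 = 0.0125 per comparison.

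**Method.** Power is for a one-sided unconditional exact test using the pooled score statistic, with the p-value maximised over the common null rate. This is the form of the planned test at zero difference. The pooled normal approximation serves as a cross-check.

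**Step 1: enrolment.** 128/0.8 = 160, 32/0.8 = 40 and 16/0.8 = 20. The sample sizes reproduce.

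**Step 2: the printed 90%.** For 16 versus 32 completers at 40% versus 5%, power at 0.0125 is 73.7% exact (76.9% pooled), so the statement does not reproduce as worded. Two variants come close to it:
- the same arms with no adjustment: 90.8% exact (89.7% pooled);
- 32 versus 32 completers, the 200/400 mg arm size, at 0.0125: 91.8% exact (89.0% pooled).

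**Step 3: the analysed set, if 5%/40% are completer rates.** Assume 20% dropout in each arm, all counted as failures:
- active: 0.8 × 40% = 32%
- placebo: 0.8 × 5% = 4%
- difference: 0.8 × 35 = 28 points

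For this analysis to show 35 points, completers would have to differ by 35/0.8, about 44 points.

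**Step 4: the analysed set, if 5%/40% are composite rates.** The rates stay at 40% and 5%, and the numbers become 20 versus 40.

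Exact power for 50 or 100 mg versus placebo:

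| Basis | 0.05 | 0.025 | 0.0125 |
|---|---|---|---|
| Completers as in 9.2: 16 v 32, 40% v 5% | 90.8% | 84.5% | 73.7% |
| mITT, completer rates diluted: 20 v 40, 32% v 4% | 87.0% | 83.1% | 71.7% |
| mITT, composite rates: 20 v 40, 40% v 5% | 94.6% | 91.5% | 84.4% |

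The pooled approximation gives 87.8% and 74.4% for the second row, and 94.4% and 85.5% for the third, at 0.05 and 0.0125.

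**Step 5: source of the gap.** Bonferroni costs 90.8 − 73.7 = 17.1 points (pooled: 89.7 − 76.9 = 12.8). Dilution costs 90.8 − 87.0 = 3.8, 84.5 − 83.1 = 1.4 and 73.7 − 71.7 = 2.0 points at the three levels.

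**Step 6: 200 and 400 mg (40 v 40) at 0.0125.** Exact power is 90.2% with diluted rates and 96.7% with composite rates (pooled: 86.3% and 95.2%). Unadjusted exact power is 97.1% and 99.3%.

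**Step 7: other rules in the documents.**
- Control-based imputation (Protocol 9.1.1), completer rates: active 0.8 × 40% + 0.2 × 5% = 33%, placebo 5%, again 28 points. Lower-dose exact power is about 85% at 0.05 and 68% at 0.0125, ignoring imputation variance.
- Three comparisons (0.05/3): lower-dose exact power is 72.7% diluted and 85.9% composite.
- Six comparisons (0.05/6), pooled: 70.0% and 82.1%. The 200/400 mg arms fall to 82.4% on diluted rates.

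**Step 8: the 128.** 160 × 0.8 = 128 is an expected value. If participants drop out independently with probability 20%, the chance of at least 128 completers is about 55%.

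**The case against.** The strongest reply is that the word completers in 9.2 qualifies the numbers, not the rates. The protocol's PASI 90 response is itself the composite, so 5% and 40% may already include dropouts. Unadjusted lower-dose power is then 94.6%. This stands. A reader might infer that the trial certainly tests a 28-point effect and misses 90% even without adjustment. The documents do not support that, because both statements need completer rates and equal 20% dropout.

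A second reply is that inflating enrolment offsets most of the dilution. Expected responders are unchanged (16 × 0.40 = 20 × 0.32 = 6.4; 32 × 0.05 = 40 × 0.04 = 1.6), and the loss is only 1.4 to 3.8 points. This also stands: dropout is not the main reason the printed figure fails.

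Third, the consequence may be slight. Protocol 4.3 projects 3% and 13% for 50 and 100 mg, so 40% at a lower dose is not expected. For 200 mg, projected at 47%, dilution gives 0.8 × 47% = 37.6% versus 4%, and exact power is still 96.7% at 0.0125. It would be wrong to extend the shortfall to the higher doses at that level by the planned exact test.

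Fourth, Hochberg is the planned procedure and never rejects less than Bonferroni. With four comparisons it rejects whenever p is at most 0.0125, and only if p is at most 0.05. Lower-dose power therefore lies between 72% and 87% on completer rates, or 84% and 95% on composite rates. On composite rates it could pass 90% if other doses also work, so the failure should be tied to the Bonferroni level in 9.2. None of these replies makes the printed statement correct.

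**Conclusion.** The point holds in limited form. The basis of the power statement does not match the primary analysis, and at the Bonferroni level that 9.2 names, the 50 and 100 mg arms have about 72% power (completer rates) or 84% (composite rates), not at least 90%. The two readings differ by about 13 points (84.4 − 71.7 = 12.7), so the missing definition matters more than dilution itself.

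The unadjusted shortfall to about 87% is conditional on completer rates and 20% dropout in every arm. It would change if some dropouts were COVID-19 discontinuations, which SAP 4.5 removes. The 200 and 400 mg arms keep about 90% or 97% at 0.0125 by the exact test. The first figure is borderline, since the pooled approximation gives 86.3%. The finding concerns a stated design property; it does not affect the validity of the primary test.

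**What to change.** Leave N unchanged.

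1. In Protocol 9.2, state whether 5% and 40% are completer rates or composite mITT rates.
2. Reconcile Bonferroni in 9.2 with Hochberg in SAP 5.1 and Appendix 3, and fix the number of comparisons.
3. Reconcile the missing-data rules in Protocol 9.1.1, Protocol 9.4.1, SAP 4.4 and SAP 4.5, so that the power basis rests on one rule.
4. Restate power by arm size on the mITT composite analysis (40 v 20 and 40 v 40) at the multiplicity level then planned. Replace the 90% claim for the lower doses with the result, which at 0.0125 is about 72% or 84%. If the rates are completer rates, give the primary-estimand effect as 32% versus 4%, 28 points.
5. In Protocol 4.1, the synopsis and SAP 2.2, describe 128 as the expected number of completers rather than a guaranteed minimum.

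The power restatement costs only text and a few figures, with no change to enrolment. Items 2 and 3 require the sponsor to choose between rules that now conflict. The stated power for the lower doses at the Bonferroni level will look less favourable.
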